12.3 Analysis Populations

The study population characteristics will be described on the Safety Population and on the Per-Protocol population. The per-protocol population will be the primary analysis set for biomarkers of exposure, clinical risk endpoints, FTND, MCEQ, Cough and QSU-brief. The Full Analysis Set will be the primary analysis set for exposure, compliance to randomization arm, Prochaska and SES. Exposure and questionnaires, as a secondary analysis, will be described by randomization arm and product used category (to be further described in the SAP) using the full analysis set.

Safety will be analyzed using the safety population.

Confidentiality Statement

Data and information contained in this document are considered to constitute trade secrets and confidential commercial information, and the legal protections provided to such trade secrets and confidential information are hereby claimed under the provisions of applicable law. No part of this document may be publicly disclosed without the written consent of Philip Morris Products S.A.

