5.3 Exploratory Objectives and Endpoints

1. To describe the following parameters in smokers switching from CC to CHTP 1.2 as compared to smokers continuing to use CC
- Excretion of mutagenic material in 24-hour urine

Endpoints:

- Ames mutagenicity test (YG1024+S9): Day 5 and Day 90 Visit.
- Subjective effects of smoking

Endpoints:

- Questionnaire of Smoking Urges (QSU), (brief version): Day 1 to Day 90 Visit.
- Fagerström Test for Nicotine Dependence (FTND), (revised version): Day 90 Visit.
- Product evaluation: Modified Cigarette Evaluation Questionnaire (MCEQ): Day 1 to Day 90 Visit.
- Cytochrome P450 2A6 (CYP2A6) enzymatic activity

Endpoints:

- the molar metabolic ratio of trans-3'-hydroxycotinine/cotinine: Day 6 and Day 90 Visit.
- Intent to Use of CHTP 1.2

Endpoints:

- Intent to Use of CHTP 1.2 Questionnaire (ITUQ): only in smokers switching from CC to CHTP 1.2: Day 6 and Day 90 Visit

2. To describe the CHTP 1.2 use over the entire exposure period according to the product preference of the subject

Endpoint (daily):

- Number of CC or CHTP 1.2 used daily as reported on the usage log during the confinement period and self-reported number of any nicotine/tobacco product use on a daily basis as reported on the product use diary during the ambulatory period according to product preference

3. To assess the smokers' mental state for the intention to quit

Endpoint (Day 90 Visit):

- Prochaska "Stage of Change" Questionnaire

4. To monitor BoExp and clinical risk endpoints in subjects who attempt to quit using tobacco products according to the time since they quit ^a

Endpoints:

- BoExp: MHBMA, S-PMA, 3-HPMA, COHb, and total NNAL
- CO (expressed as ppm) in exhaled breath
- Selected clinical risk endpoints (hs-CRP, homocysteine, blood glucose, LDL, HDL, TG, TC, fibrinogen, HbA1c, sICAM-1, WBC, platelet count, Apo A1, Apo B, 11-DTX-B2, and clinical risk endpoints related to oxidative stress) in respective body matrix

^a The reporting of the objective will be the subject of an appendix to the main clinical study report.

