**Table 9 Expected Mean Ratios and Coefficients of Variation for CHTP 1.2/CC after 90 Days of exposure**

	CHTP 1.2/CC MR (CV)
Total NNAL	0.30 (0.60)

Abbreviations: Total NNAL = Total 4-(methylnitrosamino)-1-(3-pyridyl)-1-butanol; MR = Mean ratio; CHTP 1.2 = Carbon Heated Tobacco Product 1.2; CC = Combustible cigarettes; CV = Coefficient of variation.

The power to detect a reduction was computed and is presented below.

Table 10 describes the expected power to detect a reduction of 50% or more in the levels of MHBMA, 3-HPMA, S-PMA, and COHb in CHTP 1.2 arm compared to the CC arm after 5 days of exposure and total NNAL after 90 days of exposure, with a one sided test with 2.5% type I error probability using the assumptions from YVD-CS01-EU and, and 120 randomized subjects in a 2:1 ratio (80 in CHTP 1.2 arm and 40 in CC arm). It is assumed that a minimal number of subjects will be excluded from the PP set in confinement for both arms and CC in ambulatory, whereas at least 50% will remain in the PP set in ambulatory for CHTP 1.2, therefore a 2:1 randomization ratio was chosen.

Table 10 Expected Power

Assumptions	Reduction					
	50%	51%	52%	53%	54%	55%
YVD-CS01-EU	94%	88%	81%	70%	56%	38%

The test-wise powers to detect a reduction of 50% or more in the levels of MHBMA, 3-HPMA, S-PMA, and COHb on Day 5 and in total NNAL after 90 days in smokers switching from CC to the CHTP 1.2 as compared to smokers continuing to use CC, using a one-sided test with 2.5% type I error probability using the assumptions from YVD-CS01-EU, and 120 randomized subjects in a 2:1 ratio (80 in CHTP 1.2 arm and 40 in CC arm) are described in **Table 11**.

Table 11 Test-Wise Power

Parameter	Test-Wise Power
COHb	96%
3-HPMA	>99%
MHBMA	>99%
S-PMA	>99%

Total NNAL 98%

Given the above calculation, the sample size was considered sufficient to have more than 80% power to detect a reduction of 50% or more in the levels of MHBMA, 3-HPMA, S-PMA, and COHb in CHTP 1.2 arm compared to the CC arm after 5 days of exposure, and in the levels of total NNAL in the CHTP 1.2 arm compared to the CC arm after 90 days of exposure, using a one sided test with 2.5% type I error probability.

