10 ANALYSIS POPULATIONS

The study population characteristics will be described on the Safety Population, FAS, (if different from Safety Population), and on the Per-Protocol populations for Period 1 and 4. The per-protocol populations will be the primary analysis set for biomarkers of exposure, cotinine and nicotine in plasma, CYP1A2, CYP2A6, Ames Mutagenicity test, clinical risk endpoints, FTND, mCEQ, ITUQ, Cough and QSU-brief. The Full Analysis Set will be the primary analysis set for exposure to product, compliance to randomization arm, Prochaska and SES. Exposure and questionnaires, as a secondary analysis, will be described by randomization arm and product use category using the full analysis set. If the FAS and PP population differ, the biomarkers of exposure tables will be repeated on the FAS.

Safety will be analyzed using the safety population.

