10.5 Per Protocol Populations

The PP populations are subsets of the FAS and include, by period, all randomized subjects who fulfill key compliance criteria of the protocol in the respective period, and have no major protocol deviation impacting evaluability as defined in Table 12 (see Section 11“Protocol Deviations”).

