**Table 12: Definition of Major Protocol Deviations**

Category	Description
Mis-randomization	An error in the randomization and/or product allocation process.
Product adherence	Confinement: Use of any nicotine or tobacco-containing product other than the assigned product, using the product distribution log. Ambulatory: Non-compliance in the CHTP 1.2 arm will be defined for each period. Non-compliance is based on product use reported in the product use diary for periods 2-4, as any of the following occurrences: – Use of more than 2 CC in a single day – Average product use from Day 1 through the end of the period is more than 0.5 CC per day.
Protocol violation	A deviation to the inclusion/exclusion criteria.
Procedural violation	A major deviation in the conduct of a procedure
Duration of 24 hour urine collection	Not all urine collected over 24 hours or collection period covers less than 20h or covers more than 28h for Day -2, Day -1, Day 1, Day 2, Day 3 or Day 4, Day 5/Discharge from Confinement, Day 30 Visit, Day 60 Visit or Day 90 Visit
Concomitant medication	Use of drugs which are known to affect CYP2A6 or CYP1A2 activity (except medication containing estrogen) or could interfere with clinical risk endpoints such as 11-DTX-B2..
Reporting of product use	Less than 75% of the daily product use reported in the e-diary over a period is available, or daily product use not reported over a period of more than 7 consecutive days
Visit missing	Scheduled visit not done

Subjects with violations of inclusion criteria 1, 2, 4 and 6, or of exclusion criteria 2 to 4, 15, 18 and 19 will be excluded from the PP Population. Other violations of the inclusion and exclusion criteria will be reviewed for their impact on the evaluability of the primary objectives during the pre-analysis data review meeting.

Single use of more than 2 CCs on a single day would exclude all measurements within a week after the deviation. The impacted subject would be classified as non-evaluable for the objectives assessed within a week after the deviation.

Average product use higher than 0.5 CC per day from Day 1 through an evaluation timepoint would exclude all measurements at that evaluation point. The impacted subject would be classified as non-evaluable for the objectives of the study at that evaluation point.

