15.2.5.3	Descriptive Statistics of modified Cigarette Evaluation Questionnaire Subscales – Per Protocol Population
15.2.5.4	Analysis of modified Cigarette Evaluation Questionnaire Subscales – Per Protocol Population
15.2.5.5	Descriptive Statistics of Intent to Use Questionnaire Subscales – Per Protocol Population
15.2.5.6	Descriptive Statistics of Fagerström Test for Nicotine Dependence – Per Protocol Population
15.2.5.7	Analysis of Fagerström Test for Nicotine Dependence – Per Protocol Population
15.2.5.8	Shift Table of the Prochaska Stages of Change – FAS
15.2.5.8.1	Shift Table of the Prochaska Stages of Change by Product Use Category– FAS
15.2.5.9	Descriptive Statistics of CYP2A6 Activity – Per Protocol Population
15.2.5.10	Analysis of CYP2A6 Activity – Per Protocol Population
15.2.5.11	Descriptive Statistics of Ames Mutagenicity Test (YG1024+S9) (units) – Per Protocol Population
15.2.6.1	Summary of Adverse Events – Safety Population
15.2.6.1.1	Summary of Adverse Events by Product Use Category– Safety Population
15.2.6.2	Summary of Adverse Events by System Organ Class and Preferred Term – Safety Population
15.2.6.2.1	Summary of Adverse Events by System Organ Class and Preferred Term with an incidence >5% in any Study Arm– Safety Population
15.2.6.2.2	Summary of Adverse Events by System Organ Class and Preferred Term by Product Use Category– Safety Population
15.2.6.3	Summary of Adverse Events by System Organ Class and Preferred Term by Product Use Safety Time Period– Safety Population

Tables	Title
15.2.6.4	Summary of Adverse Events by System Organ Class, Preferred Term and Relationship to Study Product Exposure for Investigational Product (CHTP 1.2 or CC) and Expectedness – Safety Population
15.2.6.5	Summary of Adverse Events Leading to Investigational Product (CHTP 1.2 or CC) Discontinuation by System Organ Class and Preferred Term – Safety Population
15.2.6.6	Summary of Adverse Events Leading to Study Discontinuation by System Organ Class and Preferred Term – Safety Population
15.2.6.7	Summary of Adverse Events Related to Study Procedure by System Organ Class and Preferred Term – Safety Population
15.2.6.8	Summary of Adverse Events by System Organ Class, Preferred Term and Severity – Safety Population
15.2.6.9	Summary of Serious Adverse Events – Safety Population
15.2.6.10	Summary of Serious Adverse Events by System Organ Class and Preferred Term and Severity – Safety Population
15.2.6.11	Summary of Clinical Chemistry Parameters – Safety Population

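### Day 90 intent to use and product evaluation of CHTP 1.2 rest mainly on per-protocol subjects, and the promised full-analysis-set description has no table

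*SAP*

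**What the plan says.** **Primary set.** SAP section 10 names the PP populations as primary for a list of endpoints that ends "clinical risk endpoints, FTND, mCEQ, ITUQ, Cough and QSU-brief". The matching list in protocol 12.3 ends "clinical risk endpoints, FTND, MCEQ, Cough and QSU-brief": it contains the mCEQ but not the ITUQ. The protocol's FAS list does not name the ITUQ either. SAP section 9, which records changes from the protocol, does not mention the ITUQ population.

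**Who is in PP.** Under SAP 10.5 the PP populations "include, by period, all randomized subjects who fulfill key compliance criteria of the protocol in the respective period". SAP Table 12 gives two ambulatory non-compliance rules for the CHTP 1.2 arm: "Use of more than 2 CC in a single day", or a mean above 0.5 CC per day counted from Day 1. It sets no ambulatory product-use limit for the CC arm. The sample-size section assumes small losses elsewhere, "whereas at least 50% will remain in the PP set in ambulatory for CHTP 1.2".

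**Secondary set.** SAP section 10 also states: "Exposure and questionnaires, as a secondary analysis, will be described by randomization arm and product use category using the full analysis set". Protocol 12.3 has the same provision.

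**Outputs.** SAP 12.5.3.1.2 places every mCEQ figure, summary and analysis on PP. In SAP 13.3.1, Tables 15.2.5.3 and 15.2.5.4 (mCEQ) are titled for PP only, as is 15.2.5.5 (ITUQ): "Descriptive Statistics of Intent to Use Questionnaire Subscales – Per Protocol Population".

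**Objective.** The ITUQ is exploratory: "Intent to Use of CHTP 1.2 Questionnaire (ITUQ): only in smokers switching from CC to CHTP 1.2: Day 6 and Day 90 Visit". SAP 7.4.5 also schedules it on Day -2.

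**The concern.** For exposure biomarkers, a PP set can be defended as describing exposure under near-exclusive use. That defence does not carry over to acceptance. A smoker who dislikes CHTP 1.2, or does not intend to go on with it, is plausibly more likely to return to cigarettes, and returning to cigarettes is what removes a CHTP 1.2 subject from PP. Membership of the set then depends, after randomization, on the attitude being measured.

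For the mCEQ at Day 90 there is a second problem. The CHTP 1.2 arm is filtered by cigarette use and the CC arm has no corresponding filter, so the contrast at that visit is not a like-for-like comparison of the randomized arms.

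The planned FAS description by product use category would let a reader see this selection. If it is not produced, the only tabulated answers on intent and liking come from the filtered subjects.

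**Working it through.** **1. How much of the arm can leave PP.** Total NNAL is the one powered endpoint that depends on the Day 90 PP share. Inputs from SAP section 8: mean ratio 0.30, CV 0.60, 50% reduction criterion, one-sided 2.5%, 80 and 40 randomized.

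- SD on the log scale = sqrt(ln(1 + 0.60²)) = 0.5545
- Distance to the criterion = ln(0.50/0.30) = 0.5108
- With 40 PP subjects in the CHTP 1.2 arm (50% of 80) and 40 CC: SE = 0.5545 × sqrt(1/40 + 1/40) = 0.1240. Power = Φ(0.5108/0.1240 − 1.96) = 98.5%, against 98% stated.
- With all 80 in PP, power would be 99.7%.

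The same method gives 95.8% for COHb at 80 vs 40 (stated 96%). Multiplying the five test-wise powers as if independent gives 94.3% with NNAL at 40 vs 40, and 95.6% with NNAL at 80 vs 40. The plan states 94%. The stated power therefore fits a design that tolerates losing 40 of 80 CHTP 1.2 subjects from the Day 90 PP set.

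**2. What the selection can do.** Let s be the PP share among CHTP 1.2 subjects who answer at Day 91, and let p_PP and p_non be the proportions giving a positive answer inside and outside PP.

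- FAS proportion = s × p_PP + (1 − s) × p_non
- Overstatement = p_PP − FAS proportion = (1 − s) × (p_PP − p_non)

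The documents give no ITUQ or mCEQ response rates. With p_PP = 0.80 assumed, the overstatement in percentage points is:

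| s | p_non 0.10 | p_non 0.20 | p_non 0.40 | p_non 0.80 |
|---|---|---|---|---|
| 0.5 | 35 | 30 | 20 | 0 |
| 0.7 | 21 | 18 | 12 | 0 |
| 0.9 | 7 | 6 | 4 | 0 |

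Only s = 0.5 comes from the plan, and there it is a floor. All the response rates are assumptions.

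**3. Whether the FAS description is delivered.**

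- SAP section 10 and protocol 12.3 promise it for questionnaires.
- SAP 12.5.3.1.2 contradicts it for the mCEQ. SAP 12.5.3.1.3 (ITUQ) names no population.
- SAP section 3 describes the SAP as listing all tables, figures and listings. In that list, among the questionnaire tables numbered 15.2.5.x, only the Prochaska tables (15.2.5.8 and 15.2.5.8.1) are on the FAS.
- The biomarker descriptive tables, by contrast, each have an FAS version.

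As listed, the answers of CHTP 1.2 subjects outside PP would appear only in Listings 15.3.5.2 (mCEQ) and 15.3.5.3 (ITUQ).

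**The case against.** The other side has several good points, and they limit what can be claimed.

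- *A reader might infer that acceptance is measured only in those who accepted the product.* The documents do not support that. The questionnaires are scheduled for all subjects who attend, and an FAS description by product use category is promised. What stands is that the promise has no table behind it.
- *A reader might infer that PP subjects by definition never went back to cigarettes.* They may smoke up to 2 CC on a day and average 0.5 CC per day, which is 0.5 × 90 = 45 CC by Day 90. The text below Table 12 removes only the week of measurements after a day above 2 CC, while the table itself defines non-compliance per period; the two need reconciling. A subject who stopped all tobacco breaches neither limit.
- *A reader might infer an artificial rise in intent from Day 6 to Day 90.* SAP 12.1.7 repeats tables that are not by period for each PP population, so a Period 4 version of Table 15.2.5.5 could show earlier assessments in the same subjects. A rise caused by changing subjects is not established.
- *A reader might take these as headline results.* No ITUQ or mCEQ table is in the topline or ClinicalTrials.gov lists. SAP section 9 makes the main mCEQ comparison the one over all time points, and five of the eight post-baseline points (Days 1 to 5) are in confinement, where few exclusions are expected.
- *A reader might want the mCEQ moved to the FAS as well.* PP is the protocol's choice for it, and its items ask about smoking and cigarettes, so subjects back on cigarettes may be rating those. That move is debatable.
- The protocol assigns the ITUQ to neither set, so the SAP fills a gap and does not reverse a stated choice. It should still be recorded.
- Subjects who miss Visit 4 have no Day 91 answer, and the FAS does not recover them.

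None of this removes the selection at Day 90 or the missing tables.

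**Conclusion.** The point holds as a should-fix on exploratory endpoints; no primary or powered analysis is affected. The Day 90 PP set in the CHTP 1.2 arm is selected on a behaviour closely linked to intent and liking, up to half of the arm may be removed, and the CC arm is not selected in the same way. Overstatement is likely. That direction rests on the assumption that subjects who return to cigarettes give less positive answers. The size is unknown: 0 if answers do not differ between the groups, 20 to 35 points at the plan's 50% floor with the assumed unequal rates, and 4 to 7 points if 90% stay in PP.

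Independently of any assumption, the SAP is inconsistent. Section 10 promises an FAS description of the questionnaires, section 12.5.3.1.2 rules it out for the mCEQ, and the output list contains no such table for either instrument.

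**What to change.** 1. In SAP section 10, make the FAS the primary set for the ITUQ, with PP supportive. This contradicts no protocol assignment and matches how the plan treats Prochaska, the other intention questionnaire.
2. Keep PP as the protocol-specified primary set for the mCEQ.
3. Add FAS versions of Tables 15.2.5.3 (mCEQ) and 15.2.5.5 (ITUQ; CHTP 1.2 arm only) by arm and product use category, with the number missing at each time point.
4. Show the ITUQ at Day -2, Day 6 and Day 91 for the same CHTP 1.2 subjects.
5. Amend SAP 12.5.3.1.2 to agree with section 10.
6. Record the ITUQ population in SAP section 9.

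The assessments are already scheduled, so the cost is SAP wording and existing table programs run on another population. The downside is a few extra tables and a possibly less favourable figure.

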10.1 Screened Population

The screened population consists of all subjects who gave informed consent.

10.2 Enrolled Population

The enrolled population consists of all subjects who were enrolled.

10.3 Randomized Population

The randomized population consists of all subjects who were randomized.

10.4 Full Analysis Set

The FAS consists of all the randomized subjects who had at least one post-randomization product use experience and have at least one valid non-safety assessment.

10.5 Per Protocol Populations

The PP populations are subsets of the FAS and include, by period, all randomized subjects who fulfill key compliance criteria of the protocol in the respective period, and have no major protocol deviation impacting evaluability as defined in Table 12 (see Section 11“Protocol Deviations”).

10.6 Safety Population

The safety population consists of all the subjects who had at least one exposure to CHTP 1.2, irrespective of whether or not the subject was exposed post-randomization. Subjects in the safety population will be analyzed according to actual exposure. The actual exposure differs from the exposure as randomized only for subjects who consistently used the wrong product; ie if the site had consistently administered the wrong product inadvertently.

10.7 Quitters Population

The quitters population consists of all subjects from the Full Analysis Set who had no CC, CHTP, e-cigarette or other tobacco products for at least 14 days prior to Discharge at Day 90 Visit or the date of early termination as reported in the product use diary.

If there are at least 10 subjects in any treatment group and timepoint who attempted to quit (see **Table 7**), the table with descriptive statistics will be repeated for that group. These tables will then get an additional “.1” to the table numbering and “by attempt to quit” will be added in the title. Subjects who restart any tobacco product use will not be included in this analysis. Otherwise, these data will be included in the listings only.

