5.2 Secondary Objectives and Endpoints

1. To evaluate self-reported nicotine/tobacco product use throughout the entire exposure period, including dual-use in an ambulatory setting in smokers switching from CC to CHTP 1.2 as compared to smokers continuing to use CC.

Endpoint (measured daily):

- Number of CC or CHTP 1.2 used daily as reported on the usage log during the confinement period, and self-reported number of any nicotine/tobacco product use on a daily basis as reported on the product use diary during the ambulatory period
2. To determine the reduction of various BoExp to HPHCs in smokers switching from CC to CHTP 1.2 as compared to smokers continuing to use CC for 5 days and for 90 days.

Endpoints (Day 5 to Day 90 Visit):

- BoExp to HPHCs in urine (expressed as quantity excreted or concentration adjusted for creatinine in 24-hour urine):
 - MHBMA (Day 90 Visit only)
 - 3-HPMA (Day 90 Visit only)
 - S-PMA (Day 90 Visit only)
 - Total NNAL (Day 5 only)

- BoExp to benzo(a)pyrene: 3-hydroxybenzo(a)pyrene (Day 5, Day 90 Visit)
 - BoExp to pyrene: total 1-hydroxypyrene (total 1-OHP) (Day 5, Day 90 Visit)
 - BoExp to N-nitrosornicotine: total N-nitrosornicotine (total NNN) (Day 5, Day 90 Visit)
 - BoExp to 4-aminobiphenyl: 4-aminobiphenyl (4-ABP) (Day 5, Day 90 Visit)
 - BoExp to 1-aminonaphthalene: 1-aminonaphthalene (1-NA) (Day 5, Day 90 Visit)
 - BoExp to 2-aminonaphthalene: 2-aminonaphthalene (2-NA) (Day 5, Day 90 Visit)
 - BoExp to o-toluidine: o-toluidine (o-tol) (Day 5, Day 90 Visit)
 - BoExp to acrylonitrile: 2-cyanoethylmercapturic acid (CEMA) (Day 5, Day 90 Visit)
 - BoExp to ethylene oxide: 2-hydroxyethylmercapturic acid (HEMA) (Day 5, Day 90 Visit)
 - BoExp to crotonaldehyde: 3-hydroxy-1-methylpropyl-mercapturic acid (3-HMPMA) (Day 5, Day 90 Visit)
 - BoExp to CO:
 - CO in exhaled breath (expressed as ppm) (Day 5, Day 90 Visit)
 - COHb in blood (expressed as % of saturation of hemoglobin) (Day 90 Visit only)
3. To describe the levels of BoExp over the entire exposure period in smokers switching from CC to CHTP 1.2 as compared to smokers continuing to use CC.
- Endpoints (Day 1 to Day 90 Visit):
- BoExp to CO:
 - CO in exhaled breath (expressed as ppm)
 - COHb in blood (expressed as % of saturation of hemoglobin)
 - BoExp to HPHCs in urine (expressed as quantity excreted and concentration adjusted for creatinine in 24-hour urine):
 - MHBMA
 - 3-HPMA
 - S-PMA
 - Total NNAL
 - Total 1-OHP
 - Total NNN
 - 4-ABP
 - 1-NA
 - 2-NA
 - o-tol

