7.5 Categorical Variables

The categorical variables used in this study are shown below (Table 7).

Table 7: Categorical Variables Definitions	
Variable	Categories
Action taken with study product due to adverse event	Product use interrupted Product use withdrawn Product use reduced None
Adverse event expectedness	No Yes
Adverse event relationship to IP	Related Not related
Adverse event relationship to Study Procedures	Related Not related
Adverse event severity	Mild Moderate Severe
Attempt to quit (based on number of days without tobacco use)	30 days ([14-44 days]) 60 days ([44-74 days]) 90 days (>74 days)
BMI (kg/m ²)	Underweight: < 18.5 Normal range: ≥ 18.5 and < 25.0 Overweight: ≥ 25.0 and < 30.0 Obese: ≥ 30.0
CO breath test level (ppm)	≤ 10 > 10
COHb level	≤ 2% > 2%
Daily CC consumption over the last 6 weeks as reported at Admission (per day).	10-19 >19
Detailed Product use Categories for CHTP 1.2 arm	Exclusive CHTP 1.2 ([95-100]%) Predominantly CHTP 1.2 ([70-95]%) Dual Mostly CHTP 1.2 ([60-70]%) Dual Balanced ([40-60]%) Dual Mostly CC ([30-40]%) Predominantly CC ([5-30]%) Exclusive CC ([0-5]%)
FTND total score	Mild: 0 – 3 Moderate: 4 – 6 Severe: 7 – 10

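### The SAP's Quitters population rests on diary self-report alone, although exhaled CO taken at the Day 90 Visit could identify subjects whose diary is contradicted

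*SAP*

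**What the plan says.** Exploratory objective 4 (SAP 5.3) is "To monitor BoExp and clinical risk endpoints in subjects who attempt to quit using tobacco products according to the time since they quit". Its endpoints are MHBMA, S-PMA, 3-HPMA, COHb, total NNAL, exhaled CO and a set of clinical risk endpoints. A footnote sends the reporting to an appendix of the study report.

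SAP 10.7 requires "no CC, CHTP, e-cigarette or other tobacco products for at least 14 days prior to Discharge at Day 90 Visit". For a subject who leaves early, the 14 days are counted back from the termination date instead. In both cases the diary is the only evidence named. SAP 5.2 describes what the diary holds: "self-reported number of any nicotine/tobacco product use on a daily basis as reported on the product use diary during the ambulatory period". On relapse, 10.7 says "Subjects who restart any tobacco product use will not be included in this analysis", without saying how a restart would be detected. The extra tables are conditional: "If there are at least 10 subjects in any treatment group and timepoint who attempted to quit"; otherwise the data are only listed. Table 7 groups quit attempts by tobacco-free days (14 to 44, 44 to 74, over 74).

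The same documents collect an objective measure. Under the schedule of assessments (Protocol Appendix A, Table A1; SAP 16.1), exhaled CO and COHb are each taken once on the first day of the Day 30, Day 60 and Day 90 Visits. Table 7 carries a CO split at 10 ppm and a COHb split at 2%. SAP 12.5.1.1 adds a flag for COHb below 2% to a listing. None of these is linked to quitter status.

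**The concern.** A subject whose diary shows 14 tobacco-free days but whose exhaled CO at the Day 90 Visit is above 10 ppm is summarised as a quitter. The plan does not accept self-report alone at entry, where Protocol section 5 requires a urinary cotinine test to verify smoking status. Yet the later claim to have stopped is not checked, although a suitable measurement is at hand.

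The trial has no abstinence arm, so these tables would be its only within-study description of what happens to the biomarkers after stopping. They may rest on as few as 10 people per group, where one or two wrongly classified subjects count.

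**Working it through.** The plan states no figure on this point, so there is nothing to reproduce. The check has three steps.

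**1. Is any biochemical condition applied?** None appears in SAP 10.7, in the quit-attempt row of Table 7, or in SAP 12.5.1.1, 12.5.2.1.1, 12.5.2.6 and 12.5.2.7, where the quitter tables are called for.

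**2. Direction and size.** Let R be the true quitters' level as a share of their usual level, and f the share of unreported smokers, assumed to stay at 100% of usual. Then:

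- geometric mean = R^(1−f) × 1^f = R^(1−f)
- arithmetic mean = (1−f)R + f

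Both exceed R whenever f > 0 and R < 1, so the decline is understated.

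R and f are assumptions. The 5%, 15% and 30% rows are illustrative values. The total NNAL rows use the half-life of 10 to 18 days in Protocol Appendix D and assume first-order elimination with no further exposure: after 14 days 0.5^(14/10) = 0.38 and 0.5^(14/18) = 0.58 remain.

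| Assumed true level R | Geometric, 1 in 10 | Geometric, 2 in 10 | Arithmetic, 1 in 10 | Arithmetic, 2 in 10 |
|---|---|---|---|---|
| 5% | 0.05^0.9 = 6.7% | 0.05^0.8 = 9.1% | (9×0.05+1)/10 = 14.5% | (8×0.05+2)/10 = 24.0% |
| 15% | 18.1% | 21.9% | 23.5% | 32.0% |
| 30% | 33.8% | 38.2% | 37.0% | 44.0% |
| 38% (NNAL, 14 days, half-life 10 days) | 41.9% | 46.1% | 44.2% | 50.4% |
| 58% (NNAL, 14 days, half-life 18 days) | 61.2% | 64.7% | 62.2% | 66.4% |

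The geometric columns matter most, because SAP 12.5.1.1 summarises the primary biomarkers on the log scale. The arithmetic columns also apply, because SAP 12.1.3 prints arithmetic means as well.

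**3. Will the tables exist?** Ten subjects are 10/40 = 25% of the planned CC arm and 10/80 = 12.5% of the planned CHTP 1.2 arm. As a simplification, the whole arm is treated as one group and timepoint. The binomial chance of at least 10 quitters, by assumed quit rate, is:

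| Quit rate | CC (n = 40) | CHTP 1.2 (n = 80) |
|---|---|---|
| 5% | 0.00002 | 0.007 |
| 10% | 0.005 | 0.28 |
| 20% | 0.27 | 0.97 |

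**The case against.** Several objections stand and shape the conclusion.

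- **Circularity.** Exhaled CO and COHb are endpoints of the same objective. Requiring low CO for entry would truncate those two tables by construction. This rules out a CO condition for the whole population, but not a check applied to the other endpoints.
- **CO does not verify the definition.** It reflects recent combustion. Protocol 4.2 gives the Day 5 biomarkers, COHb among them, an average half-life of at most 24 hours, so 14 days cannot be confirmed. E-cigarette use need not show. SAP Table 8 expects COHb on CHTP 1.2 at 0.40 of CC, so undeclared CHTP 1.2 use could pass. Table 7 does not call 10 ppm an abstinence threshold.
- **Early termination.** The early termination schedule (Protocol 9.5, Table 19) contains no CO or COHb, so that branch of the definition cannot be checked this way.
- **Weak incentive to misreport.** SAP 6.1 says quitting does not affect compensation and that other product use in the ambulatory period does not lead to discontinuation.
- **Conflicts are visible.** Listing 15.3.3.1 shows each subject's CO and COHb. A reader can see a contradiction there, but the subject stays in the summaries.

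A reader might infer that unreported smokers are in fact in these tables, or that one of them would raise a mean from 5% to 14.5%. The documents support neither as a finding. They give no misreporting rate. The 14.5% is the arithmetic mean under an assumed 5% level and a misreporter at the full usual level. That 5% does not fit total NNAL, for which the stated half-life leaves 38% to 58% after 14 days.

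**Conclusion.** The point holds as a minor, conditional one. The definition is unverified, and unreported smoking would bias the quitter tables towards a smaller decline. This requires that at least 10 subjects qualify in a group and timepoint and that some of them misreport. The first is uncertain in a population enrolled with no plan to quit within six months; on the second the documents are silent.

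On the geometric scale one misreporter in 10 has a modest effect: 5% becomes 6.7% (a decline of 93.3% instead of 95%), and 38% for total NNAL becomes about 42%. The arithmetic means shift more. All these sizes assume misreporters at their full usual level; someone secretly using CHTP 1.2 would be expected to shift most of these markers less.

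A reader might also take this as distorting a conclusion about how well cessation works. The objective is descriptive, carries no test and is confined to an appendix, so neither the primary nor any other confirmatory result is affected.

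**What to change.** Amend SAP 10.7 before database lock, which SAP section 3 allows:

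1. Keep the diary-defined set for the exhaled CO and COHb quitter tables.
2. For the other biomarkers and the risk endpoints, present the quitter tables for diary quitters with exhaled CO of 10 ppm or less on the first day of the Day 90 Visit, or add these as a CO-confirmed sensitivity set.
3. List separately the subjects whose diary and CO conflict, and early terminators with no CO value.
4. State that CO confirms only recent abstinence from combustion, not 14 days and not abstinence from CHTP 1.2 or e-cigarettes.
5. Say to which set the 10-subject rule applies.

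The cost is a few sentences and some table programming on data already collected. The confirmed group may be slightly smaller and could fall below 10, in which case those data would be listed only. Setting the rule now avoids a post-hoc decision to drop a discordant subject.
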